### *Statistical Analysis Plan*

*Analyses:* All analyses were carried out in SPSS V29.0.1.1. First, independent sample ttests were used to assess for differences in demographic and clinical variables between those who downloaded their assigned app and enrolled in the trial and those who did not, as well as between the two enrolled groups at baseline, and to compare the baseline scores of treatment completers versus individuals who dropped out of the study and failed to supply follow-up data at post-treatment.

Next, change over time both within group and between groups was examined. Analyses were completed using both per protocol (completer) and intention-to-treat (ITT) (sensitivity analysis) approaches using multiple imputation to estimate missing data. Per protocol analyses only included individuals who completed the post-treatment follow-up questionnaires. ITT (which accounts for that missing data) is generally considered the gold standard in clinical trials, especially longitudinal randomized controlled trial with missing data due to attrition [48], although it has also been criticized for being overly conservative, and for confounding the issues of acceptability and efficacy [49]. We conducted sensitivity analyses using multiple imputation to account for missing data at post-test, the only time point at which between group comparisons were possible. Because the data were missing not at random (MNAR) we used a monotone

imputation with linear regression and 5 iterations. We then analyzed the pooled data using multivariate and univariate analysis of covariance, as well as within group paired sample t-tests.

Initially, paired sample t-tests were used to examine within group change from baseline to immediate post-treatment for each group and to examine maintenance of gains from post CBT treatment to 3- and 6-months follow-up. Subsequently, multivariate and univariate general linear models were used to examine between group effects at post treatment (8 weeks), controlling for baseline levels of the dependent variables.

With respect to between group differences, we first conducted a conservative MANCOVA predicting all outcome measures (dependent variables GSRS, IBSQoL, VSI, GICog, FFQ, BDI) from the independent variable condition, controlling for all of those same measures at baseline. We then ran a series of ANCOVAs predicting each of the outcome measures individually at post-treatment from condition controlling for that measure's baseline value.

With respect to clinically significant change, we used Jacobsen and Truax's Criterion B (falling within 2 SD of the healthy mean), which is more conservative than Criterion A (falling 2 SD below the pathological mean) [50]. With respect to effect sizes, we report on partial eta squared ( $\eta^2$ ), Cohen's  $d$ , and the pooled pretest standard deviation for weighting the differences of the pre-post-means ( $d_{ppc2}$ ) [51]. The  $d_{ppc2}$  measure is designed for pre-post controlled trials where the sample sizes may be uneven across groups, as was the case in our data set.

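### The SAP gives MNAR as the reason for an imputation that assumes MAR, so neither post-treatment analysis addresses MNAR and their agreement gives no reassurance

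*SAP*

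**What the plan says.** All of this is in the SAP under Statistical Analysis Plan, Analyses, mostly in the second paragraph.

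- **Two analyses.** "Analyses were completed using both per protocol (completer) and intention-to-treat (ITT) (sensitivity analysis) approaches using multiple imputation to estimate missing data". The role of imputation is repeated: "We conducted sensitivity analyses using multiple imputation to account for missing data at post-test".
- **The completer set.** "Per protocol analyses only included individuals who completed the post-treatment follow-up questionnaires". No adherence or app-use criterion is given.
- **The view of ITT.** "ITT (which accounts for that missing data) is generally considered the gold standard in clinical trials", with the qualification "although it has also been criticized for being overly conservative, and for confounding the issues of acceptability and efficacy".
- **Mechanism and method.** "Because the data were missing not at random (MNAR) we used a monotone" "imputation with linear regression and 5 iterations". No predictors are listed. No shift, pattern-mixture, selection-model or tipping-point step is described.
- **Attrition check.** The first paragraph plans to "compare the baseline scores of treatment completers versus individuals who dropped out of the study".
- **Models.** The last paragraph of Analyses starts with a MANCOVA adjusted for all six baseline measures. ANCOVAs follow, each adjusted only for its own baseline. Imputed data are analysed with the same types of model.

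**The concern.** The stated reason does not lead to the stated method. Monotone describes the pattern in which values are missing, not why they are missing. Regression imputation draws missing scores from a model fitted to people who were observed, so it treats dropouts as exchangeable with observed people who have the same predictors. MNAR says that they are not.

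The completer analysis makes much the same assumption. A reader who sees the completer and imputed results agree may conclude that attrition has been dealt with. If dropout depends on the unseen post-treatment score, and does so differently or at different rates in the two arms, both analyses can show an effect that does not exist.

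**Working it through.** The SAP states no dropout rate, sample size or effect size, so there is no figure to reproduce. The check compares assumptions and then illustrates the size of the problem.

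**Step 1. What each analysis needs.** Let Y be the post-treatment score, X the modelled baseline(s) and Z condition.

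- Completer model: Y = a + bX + cZ + error, fitted where Y is observed. The estimate of c is unbiased if, given X and Z, the chance of observing Y does not depend on Y.
- Regression imputation: the same kind of model is fitted to observed Y, and missing Y is drawn from it. The condition is the same, given the imputation predictors.
- MNAR denies that condition. The comparison of completers and dropouts at baseline can argue against missing completely at random. It cannot separate MAR from MNAR, because the score in question is unseen.

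**Step 2. Size of the shared bias.** All inputs are assumed: no true effect, baseline-outcome correlation 0.6, higher score = worse, logit(dropout) = constant + sY with slope s per SD, and the constant set to give the stated dropout. Bias is in SD units from 1,000,000 per arm. False-positive rates (nominal 5%) come from 2,000 simulated trials with 20 imputations, at 60 and 100 per arm.

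| Dropout, arm A v B | s, A / B | Bias, completer ANCOVA = imputation on same covariates | Bias, imputation on six baselines | False positives, completer (60, 100) | False positives, imputed (60, 100) |
|---|---|---|---|---|---|
| 30% v 30% | 0.7 / 0.7 | 0.000 | 0.000 | 5.9%, 5.9% | 5.9%, 5.9% |
| 30% v 20% | 0.7 / 0.7 | -0.042 | -0.040 | 5.8%, 5.5% | 6.0%, 5.1% |
| 40% v 20% | 0.7 / 0.7 | -0.078 | -0.074 | 7.5%, 9.6% | 7.2%, 9.1% |
| 30% v 30% | 0.7 / 0 | -0.124 | -0.118 | 10.8%, 15.3% | 10.8%, 14.7% |
| 40% v 20% | 0.7 / 0 | -0.166 | -0.158 | 15.7%, 22.2% | 15.1%, 21.4% |
| 40% v 20% | 1.0 / 0 | -0.216 | -0.207 | 23.4%, 36.3% | 22.3%, 35.2% |

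Hand check: let g be the amount by which the true missing scores are worse than the imputed ones. Then bias ≈ -(d_A g_A - d_B g_B), where d is the dropout proportion. Row 4 gives g = 0.124/0.30 = 0.41. With g = 0.41 in both arms, row 2 should be about -0.41 × (0.30 - 0.20) = -0.04, row 3 about -0.41 × 0.20 = -0.08, and row 1 zero. With g = 0.41 in arm A only, row 5 should be about -0.40 × 0.41 = -0.16. All agree with the table. Row 6 implies g = 0.216/0.40 = 0.54.

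A separate simulation (correlation 0.5, slope 1 in both arms, 40% v 20%) gave -0.125 for completers and -0.126 for imputation. When dropout depended only on the outcome's own baseline (MAR), both were within 0.01 of zero.

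**Step 3. What a delta analysis shows.** Worsening the imputed scores by δ moves the estimated effect by d_A δ_A - d_B δ_B. In the row 6 setting, with δ in arm A only, each step of 0.2 moves it by 0.40 × 0.2 = 0.08:

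| δ | Bias, 60 per arm | False positives | Bias, 100 per arm | False positives |
|---|---|---|---|---|
| 0 | -0.221 | 22% | -0.219 | 35% |
| 0.2 | -0.141 | 11% | -0.138 | 17% |
| 0.4 | -0.061 | 6% | -0.057 | 7% |
| 0.6 | 0.019 | 5% | 0.023 | 5% |

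A wrong δ does harm. In the row 1 setting, δ = 0.6 in one arm alone creates a bias of about 0.30 × 0.6 = 0.18. The simulation gave 0.19 and 0.18 SD, with 18% and 26% false positives at 60 and 100 per arm.

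**Step 4. Dropout that depends on another baseline measure W.** The same rates and slopes were applied to W instead of Y. The single-baseline completer ANCOVA was biased by at most 0.033 SD when W correlated 0.4 with the outcome and 0.5 with its own baseline, and by up to 0.108 SD at 0.5 and 0.3. Imputation that included W was within 0.004 SD of zero. A completer model with W added as a covariate also had a bias of about 0.004 SD or less. This measures the covariate set, not completer against ITT.

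**The case against.** **MNAR may simply be a misused word.** This stands in part. If missingness is in fact MAR given baseline and condition, both analyses are sound for the between-group contrast, and correcting the sentence would remove the contradiction. But the observed data cannot show which mechanism holds, so a check of departures from MAR is still worth having.

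**The sizes are assumed.** This stands. With the same mechanism in both arms, false positives stay between about 5% and 10%. At 100 per arm, the rates from about 15% to 36% all need outcome-dependent dropout in one arm only. A reader might infer unequal dropout from the SAP's remark, under effect sizes, that group sizes were uneven. The SAP gives no cause for that, so the inference is not supported.

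**The ranking is inferred.** A reader might conclude that the completer analysis is the primary one. Labelling ITT a sensitivity analysis points that way, but the SAP never uses the word primary and says that both analyses were done. Nor would promoting the imputed analysis address MNAR: Step 2 shows the same bias in both.

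**Single-baseline ANCOVAs do not condemn the completer approach.** This stands. The MANCOVA already adjusts for all six baselines, so only the follow-up ANCOVAs are exposed to dropout that depends on another of these measures. Adding those baselines as covariates would remove that bias as well as imputation does.

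**The 'per protocol' label is openly defined.** This stands. The word completer sits beside the label and the entry rule follows, so nothing is concealed. The SAP reports a criticism of ITT about acceptability and efficacy, but does not claim that the completer set separates the two.

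**Conclusion.** The point holds in a limited form. The SAP asserts MNAR, offers it as the reason for a method that assumes MAR, and describes no analysis that departs from MAR. Under the asserted mechanism the completer and imputed results can carry the same bias, and their agreement would not show robustness.

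Under the assumed inputs the shared between-group bias runs from 0.00 to about 0.22 SD. Imputing from all six baselines lowers it by at most about 0.01 SD in the scenarios tabulated. These figures show what is possible. They do not show that this trial's results are biased, and the document gives no basis for saying so.

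The ranking and the label are secondary. The SAP's own description of ITT under attrition sits awkwardly with calling it a sensitivity analysis, and entry to the 'per protocol' set depends only on questionnaire return. Changing either improves the presentation but does not deal with MNAR. The matter should be fixed; confidence is moderate because no dropout data are given.

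**What to change.** 1. **Correct the rationale.** Replace the MNAR justification with a statement that the imputation assumes MAR given condition and all six baseline measures, and include these in the imputation model.
2. **Add a tipping-point analysis of the post-treatment ANCOVAs.** Worsen imputed scores by 0, 0.2, 0.4 and 0.6 baseline SD, in each measure's direction of worse, in both arms and in each arm alone. Report for each outcome the delta at which its conclusion changes. Present this as a check and not as a correction, because the true delta is unknown.
3. **Secondary: ranking.** Present the imputed analysis in the assigned groups as the leading between-group result. The SAP is written in the past tense, so report this as post hoc if the analyses have been run.
4. **Secondary: label.** Call the 'per protocol' set completer (available-case) and keep it as supportive.

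**Cost.** The work is wording and a rerun on data already held: one setting at delta 0 plus 3 deltas × 3 arm choices = 10 settings, or 60 ANCOVAs for six outcomes. In the simulations, standard errors rose by about 1 to 2% for imputation without delta (0.174 to 0.177 is 1.7%) and by about 5% with delta 0.6 in both arms (0.171 to 0.180 is 5.3%). Some deltas may give less favourable results.

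### The SAP justifies its regression imputation by saying the data are MNAR, but that imputation assumes MAR, so either the label is wrong or the sensitivity analysis misses its target.

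*SAP*

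**What the plan says.** All of this is in the SAP, section Statistical Analysis Plan, under Analyses.

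- **Two approaches.** "Analyses were completed using both per protocol (completer) and intention-to-treat (ITT) (sensitivity analysis) approaches using multiple imputation to estimate missing data". The completer set is defined by response: "Per protocol analyses only included individuals who completed the post-treatment follow-up questionnaires".
- **Role of the imputation.** "We conducted sensitivity analyses using multiple imputation to account for missing data at post-test", a time point described as "the only time point at which between group comparisons were possible".
- **Mechanism and method, in one sentence.** "Because the data were missing not at random (MNAR) we used a monotone" "imputation with linear regression and 5 iterations".
- **Use of the imputed data.** "We then analyzed the pooled data using multivariate and univariate analysis of covariance, as well as within group paired sample t-tests".
- **Only described check that bears on dropout.** Independent-sample t-tests "compare the baseline scores of treatment completers versus individuals who dropped out of the study".

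The SAP mentions no delta shift, pattern-mixture model, selection model or reference-based imputation.

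**The concern.** The sentence gives a mechanism as the reason for a method that assumes a different mechanism. A monotone pattern can arise under MCAR, MAR or MNAR, so MNAR is no reason to choose a monotone algorithm. Linear-regression imputation fits a model to the participants who responded and draws the missing scores from it. That is right only if, given the predictors, non-responders are distributed like responders, which is MAR. If the data are MNAR, this condition fails by definition.

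Two readings remain, and the text does not decide between them:

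1. **Mislabel.** Dropouts may have differed from completers at baseline, and this was called MNAR. Such a difference argues against MCAR but cannot establish MNAR, which concerns the scores nobody saw.
2. **MNAR is meant.** Then the one analysis offered as a check on the completer result assumes away the problem the SAP declares.

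At stake is how the imputed (ITT) result may be read at the single time point with a between-group comparison. A reader who sees completer and imputed analyses agree will take it as robustness to dropout. On the second reading that inference is not available.

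**Working it through.** The SAP states no figure on this point, so there is none to reproduce. The question is how regression imputation behaves under each mechanism.

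**Inputs, all assumed.** Standard normal baseline x and post score y (higher = worse), correlation r = 0.6, no true effect and no true change. Dropout is logistic, logit P(drop) = a + g·y, with g = 0.5 to 1.0 per SD of the unseen post score and a set to give the stated dropout rate p. Imputation uses baseline and condition. Negative bias favours the arm with more dropout, or with the only informative dropout.

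**Step 1: first-order formulas.** The residual variance of y given x is 1 - r² = 1 - 0.36 = 0.64. To first order in g, observed scores at a given baseline lie g·p·(1 - r²) below the full-population mean. Therefore:

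- between-group ANCOVA bias ≈ -(1 - r²)·(g1·p1 - g0·p0);
- within-group change, imputed ≈ -g·p·(1 - r²);
- within-group change, completers ≈ -g·p·(1 - r).

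The imputation draws from the same fitted line as the completer ANCOVA, so it carries the same between-group bias.

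**Step 2: between-group bias (SD), g = 0.5 / 1.0.** The simulation used at least 1 million per arm. Completer and imputed ANCOVA agreed to about 0.001 SD.

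| Dropout | Formula | Simulated, both analyses |
|---|---|---|
| 30% vs 30% | 0 / 0 | 0.00 / 0.00 |
| 25% vs 20% | -0.64·0.5·0.05 = -0.016 / -0.032 | -0.02 / -0.03 |
| 30% vs 20% | -0.64·0.5·0.10 = -0.032 / -0.064 | -0.03 / -0.05 |
| 40% vs 20% | -0.64·0.5·0.20 = -0.064 / -0.128 | -0.06 / -0.11 |
| 40% informative vs 20% not | -0.64·0.5·0.40 = -0.128 / -0.256 | -0.12 / -0.22 |

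The formula overshoots somewhat at g = 1.0, as a linear approximation does. With six outcomes imputed from all six baselines and condition (within-time correlation 0.3 or 0.5), the two analyses still differed by at most 0.002 SD. This could change if dropout depended directly on other baseline measures. A separate simulation with n = 300, a true effect of -0.50 SD and informative dropout in the active arm only gave -0.60, -0.66 and -0.70 for both analyses at g = 0.5, 1.0 and 1.5. Under MCAR and MAR both returned -0.50.

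**Step 3: false-positive rates.** Assumed 70 per arm, 5 imputations, 3,000 replicates, nominal 5%. The range covers g = 0.5 to 1.0.

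| Dropout | Completer | Imputed | Both significant |
|---|---|---|---|
| 30% vs 30% | 4-5% | 5% | 3% |
| 30% vs 20% | 6% | 5-6% | 4-5% |
| 40% vs 20% | 6-10% | 6-10% | 4-7% |
| One arm informative | 11-27% | 10-24% | 8-21% |

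**Step 4: within-group change at 30% dropout.**

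- Imputed, formula: -0.5·0.3·0.64 = -0.096 and -1.0·0.3·0.64 = -0.192. Simulated: -0.09 and -0.17.
- Completers, formula: -0.5·0.3·0.4 = -0.06 and -1.0·0.3·0.4 = -0.12. Simulated: -0.06 and -0.10.
- If dropout depends only on baseline (MAR; slopes 0.29 and 0.53): imputed 0.00, completers +0.03 and +0.06, between-group bias 0.

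**Step 5: can the dropout check tell the mechanisms apart?** At 30% dropout, MNAR slopes of 0.5 and 1.0 put dropouts 0.29 and 0.51 SD worse at baseline than completers. MAR dropout with baseline slopes of 0.29 and 0.53 gives the same gaps. The same t-test result is thus compatible with zero bias and with the biases in Step 2.

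**The case against.** The strongest reply is that this is a wording error with little built on it. If MNAR was a slip, one sentence changes and no result moves. A mislabel is plausible, and the SAP never says the completer-dropout t-tests were the basis for the MNAR statement. All of that is fair, but the sentence is still wrong on that reading, and the text does not show that it is the right one.

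The numbers can also be attacked. None of the inputs comes from the SAP. At 25% vs 20% and 30% vs 20% dropout the bias is at most about 0.05 SD, and at 30% vs 20% false positives stay at 5-6%. The large values need dropout that is very unequal and informative in one arm only. The direction is unknown too and could work against the CBT arm. The SAP does say, in its effect-size paragraph, that the groups were uneven, but not whether this arose at enrolment or through dropout; the 70-per-arm figures do not reflect it. These limits stand, and they are why the point is worth correcting but not critical.

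Two narrower objections also hold:

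- With condition and baseline as predictors, imputed and completer ANCOVA nearly coincide under any mechanism. Their agreement is uninformative about MNAR whatever the label; under MAR both are simply unbiased. Relabelling makes the claim honest, not the check stronger.
- The within-group ranking in Step 4 depends on the dropout model. If dropout follows lack of improvement (post minus baseline, same slopes per SD of change), completers give -0.13 and -0.22 and imputed -0.10 and -0.18, so the imputed result is closer to the truth. Neither analysis is generally the safer one under MNAR.

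**Conclusion.** The concern holds. As written, the stated mechanism and the chosen method contradict each other, and nothing else in the SAP supplies a departure from MAR. This does not depend on any assumed figure.

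The effect on the results cannot be derived from the SAP. Under the assumed dropout model it runs from nothing (equal, equally informative dropout) through a few hundredths of an SD (modest imbalance) to about 0.2 SD (40% vs 20%, informative in one arm only, the least favourable case examined). Throughout that range the imputed ANCOVA neither removes nor reveals the bias, provided it uses condition and the baseline measures. If MAR given those predictors is what the authors mean, the imputed analysis is sound and only the rationale needs correcting. The point should be fixed; it does not by itself overturn a result.

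**What to change.** Choose one of two edits:

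1. **If MAR is meant:** state that the regression imputation assumes the post-treatment scores are missing at random given the imputation predictors, and delete the MNAR rationale. Present monotone only as the missingness pattern.
2. **If MNAR is meant:** keep the imputation as the MAR reference and add a delta-adjusted tipping-point analysis. Shift the imputed post-treatment scores toward worse, separately by arm, in growing steps, and report the shift at which each between-group conclusion is lost. To first order the shift needed is g·(1 - r²), that is 0.5·0.64 = 0.32 SD and 1.0·0.64 = 0.64 SD. In simulation, shifts of about 0.31 and 0.56-0.58 SD brought the between-group bias to 0.00, so the grid should extend beyond 0.6 SD. Other analyses that depart from MAR, such as pattern-mixture or selection models, would also serve. The SAP is written in the past tense, so if the analyses are done the addition should be labelled post hoc.

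As tidying in the same edit, name the imputation predictors, including condition and the baseline measures, and say whether the 5 iterations are 5 imputed datasets.

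The cost is one sentence for the first option and a modest extra analysis for the second, with no new data. The downside is that results may look less robust.

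### The SAP gives a single-pass monotone imputation five iterations; if five imputed data sets are meant, a borderline ITT p-value can fall on either side of 0.05 depending on the seed

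*SAP*

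**What the plan says.** Everything on this point stands in the Analyses text of the SAP's Statistical Analysis Plan section.

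- **Role of the imputation:** "Analyses were completed using both per protocol (completer) and intention-to-treat (ITT) (sensitivity analysis) approaches using multiple imputation to estimate missing data". The imputed analysis is the plan's only ITT analysis, and it is labelled a sensitivity analysis beside the completer analysis.
- **What is imputed:** "We conducted sensitivity analyses using multiple imputation to account for missing data at post-test, the only time point at which between group comparisons were possible".
- **Method:** "Because the data were missing not at random (MNAR) we used a monotone" "imputation with linear regression and 5 iterations".
- **Use of the imputed data:** "We then analyzed the pooled data using multivariate and univariate analysis of covariance, as well as within group paired sample t-tests".
- **Software:** "All analyses were carried out in SPSS V29.0.1.1".

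The figure 5 is attached to iterations. The SAP does not state a number of imputed data sets (m), a random seed or a pooling rule. Its closing paragraph, on clinically significant change and effect sizes, adds nothing on imputation.

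**The concern.** Iterations belong to chained (fully conditional) imputation, where the variables are cycled through until the draws settle. A monotone method orders the variables by missingness and imputes each one once from those already complete, so there is no chain to run. Read literally, the sentence does not define a procedure that a second analyst could repeat. The natural reading is that 5 is the number of imputed data sets.

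On that reading the number is low for the use made of it. The ITT analysis is there to show whether the completer conclusions survive once missing data are accounted for, and in practice that comparison is made on p-values. With m = 5 the variance between imputations is estimated on 4 degrees of freedom, and the pooled estimate itself shifts from one set of draws to the next. If a result lies near 0.05, the random draw can decide whether the ITT analysis appears to support the completer analysis.

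**Working it through.** **Is there a figure to reproduce?** No. The 5 is a setting, and the SAP gives no sample size, attrition, effect size or alpha. The check therefore asks what m = 5 implies over a range of assumed conditions.

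**Inputs from the SAP:** monotone linear-regression imputation of post-test scores; the number 5, read as m; and ANCOVAs "predicting each of the outcome measures individually at post-treatment from condition controlling for that measure's baseline value".

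**Assumptions, not in the SAP:** 100 participants in two equal arms, baseline-outcome correlation 0.6, dropout of 10% to 50% and equal in both arms, and an effect set so that the completer z is 2.1 (p about 0.04).

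**Step 1, efficiency.** Let FMI be the fraction of missing information. Relative efficiency = 1/(1 + FMI/m). At m = 5:
- FMI 0.1: 1/1.02 = 0.98
- FMI 0.3: 1/1.06 = 0.94
- FMI 0.5: 1/1.10 = 0.91

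The standard error rises by a factor of √1.02 to √1.10, that is, by 1% to 5%. The point estimate loses little.

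**Step 2, analytic seed-to-seed spread.** The SD over seeds of the pooled z is about √(FMI/m). Take a result at z = 2.0 (p = 0.046) with m = 5, and use z ± 1.96 SD:
- FMI 0.1: SD = √0.02 = 0.14; p from 0.023 to 0.085
- FMI 0.3: SD = √0.06 = 0.24; p from 0.013 to 0.129
- FMI 0.5: SD = √0.10 = 0.32; p from 0.009 to 0.168

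For a clear result, z = 4 with FMI 0.3, the range is 4 ± 1.96 × 0.245, or 3.5 to 4.5. The p-value stays below 0.001 throughout.

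**Step 3, simulation.** One data set was held fixed at each dropout rate. The post-test score was imputed by Bayesian linear regression on condition and baseline, analysed by ANCOVA, and pooled by Rubin's rules with Rubin's original degrees of freedom. Only the seed varied (1,000 seeds for m = 5; 300 for m = 50 and m = 100). Each cell gives the central 95% of pooled p-values and, in brackets, the share of seeds with p < 0.05.

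| Missing | m = 5 | m = 50 | m = 100 |
|---|---|---|---|
| 10% | 0.017–0.085 (75%) | 0.028–0.046 (99.7%) | 0.030–0.043 (100%) |
| 30% | 0.006–0.180 (52%) | 0.021–0.064 (85%) | 0.026–0.054 (93%) |
| 50% | 0.003–0.252 (46%) | 0.021–0.081 (71%) | 0.024–0.068 (78%) |

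The simulated ranges at 30% and 50% are wider than those in step 2, which does not allow for seed-to-seed variation in the pooled standard error. With 200 participants the m = 5 ranges are almost the same: 0.018–0.087, 0.007–0.180 and 0.003–0.251.

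**Step 4, dependence on the starting point.** A second simulation took 50 per arm, 30% missing, correlation 0.6, and a data set whose p-value with 1,000 imputations is 0.03. Five imputations gave p from 0.006 to 0.16, with 37% of seeds non-significant; 50 imputations gave 0.020 to 0.051, with 3%. In step 3 the corresponding non-significant shares are 48% and 15%. The width of the range is similar, but the share crossing 0.05 depends heavily on how near to 0.05 the case lies.

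**The case against.** **The word is a slip, and m = 5 is never stated.** This is fair. That 5 means imputed data sets is an inference. If it is wrong, the sentence carries a setting with no meaning for its method and leaves m open, so the text still needs correcting.

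**The borderline case was chosen.** This is also fair. The figures show what happens near p = 0.04, and the SAP gives no result to show whether any outcome lies there. The ranges apply to borderline results only.

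**It is only a sensitivity analysis.** This limits the weight of the point. It does not remove it, because no other ITT analysis is planned.

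**Stronger readings that the SAP does not support.**
- *That attrition is heavy.* A reader might infer this from the presence of a separate ITT analysis, or from the phrase "especially longitudinal randomized controlled trial with missing data due to attrition". That phrase describes trials in general, and the SAP justifies ITT by its standing as a method. No dropout figure for this trial is given.
- *That the ITT results cannot be reproduced.* A recorded seed reproduces an analysis exactly at any m, and the SAP's silence does not show that none was set. The fault is instability across seeds, which is a different matter.
- *That the tests are invalid or lose real power.* Rubin's degrees of freedom already allow for few imputations; at large sample they are 4/FMI², or 44 at FMI 0.3 and 16 at FMI 0.5. The efficiency loss in step 1 is small.
- *That every ITT p-value is exposed to the same degree.* Only an ANCOVA was simulated. Nothing was computed for the MANCOVA or the paired t-tests.

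**Conclusion.** The point holds in a limited form. The stated setting does not fit a monotone method, and the SAP gives neither a number of imputed data sets nor a seed. If five imputed data sets are meant, a borderline ITT result can be significant or not according to the seed. With 30% missing and a completer p of about 0.04, about half the seeds fall on each side of 0.05 (52% below, 48% not). At 10% missing the range is narrower but still spans 0.05.

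These sizes rest on assumed sample size, correlation, dropout and closeness to 0.05, none of which the SAP supplies. The problem is Monte Carlo noise, not bias. It does not touch the completer analysis or any clear ITT result. It is worth correcting because it affects the plan's only ITT analysis and costs almost nothing to put right.

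**What to change.** Replace the reference to five iterations with: *m = 100 imputed data sets, with a fixed, recorded random seed*. Then rerun the pooled ITT analyses. The cost is one line of SAP text and a few minutes of computing, with no new data.

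Some noise remains if much is missing: at 50% missing, even m = 100 leaves p between 0.024 and 0.068 in the borderline case above. A result that close to 0.05 should be described as borderline whatever the seed gives.

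The change does not address a separate fault in the same sentence. MNAR is given there as the reason for a regression imputation that assumes missing at random, and no increase in m or fixing of the seed cures that.
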